- Subjects with prior treatment for PCa including BT, RT or hormone therapy.

c) Number of Subjects:

This is a 3+3 dose escalation design study to determine the MTD. This study will use 2 dose levels and 1-6 subjects at each dose level. The first subject enrolled at each dose level (60 and 75 Gy) will be monitored for the entire DLT window (3 months post EBRT completion) with subsequent subjects enrolled either at the same dose (if only 1 of the first 3 subsequent subjects at the given dose experiences DLT) or in the

[Type here]

Protocol Title:	A Phase I Single-Arm Open Label Dose-Escalation Study of CivaSheet with Radical Prostatectomy with or without Adjuvant External Beam Radiation Therapy in Patients with High Risk Prostate Cancer
Principal Investigator Name/Contact Info:	[name]/ [contact]/ [contact]
Primary Contact Name/Contact Info	[contact] [name]
Date Revised:	7/22/2022
Study Number:	GCO#1: 16-1314

next dose level if the preceding dose is deemed acceptable (i.e., < 33% DLT within 90 days post EBRT). If in the first subject, Grade 4-5 hematuria, fistula formation, proctitis or death occurs in the DLT window, the trial will be terminated. The total number of subjects for this single arm 3+3 trial design is therefore a minimum of 1 and a maximum of 12.

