The dose escalation design utilized for the present study will proceed as follows: The first subject will be enrolled at 60 Gy. Once the entire DLT window (i.e., 90 days post EBRT) is complete for this first subject, the next 2 subjects will be enrolled at 60 Gy. If in the first subject, grade 4 or higher hematuria, proctitis, fistula formation or death occurs in the DLT window, the trial will be terminated. If 2 of the first 3 subjects experience DLT at 60 Gy, the trial will be terminated. If 0 or 1 of the first 3 subjects enrolled at 60 Gy experience a DLT after the third subject's entire DLT window is complete, an additional three subjects will be enrolled at 60 Gy. If $\geq 33\%$ of subjects experience DLT at 60 Gy, the trial will be terminated. If after the sixth subject's DLT window is complete and < 33% of subjects experience DLT at 60 Gy, the first subject at 75 Gy will be enrolled. Once the entire DLT window (i.e., 90 days post EBRT) is complete for this first subject at 75 Gy, the next two subjects will be enrolled at 75 Gy. If in the first subject at 75 Gy, grade 4 or higher hematuria, fistula formation, proctitis or death occurs in the DLT window, 60 Gy will be considered the MTD and no additional subjects will be enrolled at 75 Gy. If 2 of the first 3 subjects experience DLT at 75 Gy, 60 Gy will be considered the MTD and no additional subjects will be enrolled at 75 Gy. If 1 or 0 of the first 3 subjects enrolled at 75 Gy experience a DLT after the third subject's entire DLT window is complete, an additional 3 subjects will be enrolled at 75 Gy. If $\geq 33\%$ of subjects experience DLT at 75 Gy, no additional subjects will be enrolled at 75 Gy and 60 Gy will be considered the MTD. If after the sixth subject's DLT window is complete and < 33% of subjects experience DLT at 75 Gy, 75 Gy will be considered the MTD.

The true risk of toxicity is expected to be in the range of 10-50%. The following table shows the corresponding probabilities of dose escalation.

True Risk of Toxicity	0.1	0.2	0.3	0.4	0.5
Probability of Escalation	0.96	0.87	0.69	0.50	0.31

[Type here]

Protocol Title:	A Phase I Single-Arm Open Label Dose-Escalation Study of CivaSheet with Radical Prostatectomy with or without Adjuvant External Beam Radiation Therapy in Patients with High Risk Prostate Cancer
Principal Investigator Name/Contact Info:	[name]/ [contact]/ [contact]
Primary Contact Name/Contact Info	[contact] [name]
Date Revised:	7/22/2022

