Study Number:	GCO#1: 16-1314

A minimum of 3 and a maximum of 6 subjects within a dose level must be observed for one cycle (90 day post EBRT completion) before accrual to the next higher dose level may begin.

Three patients within a dose level must be observed for one cycle (30 days post EBRT) before accrual to the next higher dose level may begin. The treatment for this study is RP + Civasheet implant + adjuvant EBRT for patients with high-risk or intermediate (non-clinically localized) prostate cancer with adverse pathologic features including seminal vesicle invasion, extra prostatic extension or a positive surgical margin. Since the clinical guidelines recommend adjuvant EBRT post RP only for patients with adverse pathologic features at RP, patients without these adverse pathologic features at RP will be replaced with additional patients at that dose level. Since however eligibility criteria is for high risk or non-clinically localized intermediate risk prostate cancer, the anticipated number of patients without these adverse pathologic features who will not receive adjuvant EBRT is 2 or less. While toxicities among these patients will be monitored according to the protocol, toxicities among these patients will not be used in determinations of the MTD. The MTD will only be determined for patients undergoing RP + Civasheet implant + adjuvant EBRT.

If a subject is withdrawn from the study prior to completing the entire cycle of therapy or prior to completing the entire DLT window without experiencing a DLT prior to withdrawal, an additional subject may be added to that dose level. Subjects missing doses due to a DLT will not be replaced since these subjects will be considered to have experienced a dose limiting toxicity.

d) Study Timelines:

The duration of an individual subject's participation in this study including follow-up is 5 years.

The expected duration for the investigators to complete this ranges between 1 month for a minimum of 1 subject and 44 months for a maximum of 12 subjects.

Table 1. Time and events table for those undergoing RP + Civasheet implant + adjuvant EBRT.

[Type here]

Effective Date: 10/18/2022

End Date: 10/17/2023

Protocol Title:	A Phase I Single-Arm Open Label Dose-Escalation Study of CivaSheet with Radical Prostatectomy with or without Adjuvant External Beam Radiation Therapy in Patients with High Risk Prostate Cancer									
Principal Investigator Name/Contact Info:	[name]/ [contact]/ [contact]									

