Adverse events, complication, toxicity and subject compliance with the protocol will be monitored. Adverse events related to surgery will be graded using the Dino-Clavien grading system. As per standard care, standard side effects of surgery including but not limited to fever, chills, nausea, vomiting, abdominal pain, constipation, incontinence will be monitored and appropriate therapy implemented. The adverse events for surgery we monitor include infection, stricture, abscess, bowel perforation, erosion into surrounding structures, bleeding, fistula, worse rates of continence and erectile function. Adverse events and toxicity associated with radiation we monitor include GI and GU toxicity, bladder and rectal adverse effects, urethral strictures, hematuria, radiation proctitis. All toxicity will be graded according to the RTOG acute and late morbidity scoring schemes. The adverse events related to the implementation of the Civasheet® include radiation to other areas due to movement of the sheet which will be monitored with a 30 day post implant CT to ensure stability of the device and implant method for all patients and additionally at 90 days and at 6 months for those undergoing EBRT. To ensure subject compliance, subjects will be counseled each visit or phone call as on the adherence to study criteria. Subject failure to follow up or comply with protocol as well as the reasons for failure to follow up or comply with protocol will be assessed and documented.

Type here]

Protocol Title:	A Phase I Single-Arm Open Label Dose-Escalation Study of CivaSheet with Radical Prostatectomy with or without Adjuvant External Beam Radiation Therapy in Patients with High Risk Prostate Cancer
Principal Investigator Name/Contact Info:	[name]/ [contact]/ [contact]
Primary Contact Name/Contact Info	[contact] [name]
Date Revised:	7/22/2022
Study Number:	GCO#1: 16-1314

Adverse events and toxicity will be monitored and assessed at each follow-up visit or phone call for all subjects enrolled. After the first subject's DLT window is complete at 60 Gy (90 days post-EBRT), we will make a decision to enroll additional subjects at 60 Gy only if Grade 4-5

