hematuria, proctitis, or fistula are not observed. If 2 additional subjects are enrolled at 60 Gy, we will review for DLTs after completion of the 90 day DLT window and enroll 3 additional subjects at 60 Gy if DLT has been observed in 1 subject, or enroll 1 subject at 75 Gy if no DLT were observed or terminate the trial if $\geq 33\%$ DLT were observed in all subjects. For the next group of subjects at 60 Gy, we will review DLT/toxicity after all three subjects have completed the 90 days DLT window after EBRT. After the first subject's DLT window is complete (90 days post-EBRT) at 75 Gy, we will make a decision to enroll additional subjects at 75 Gy only if Grade 4-5 hematuria, proctitis, or fistula are not observed. If 2 additional subjects are enrolled at 75 Gy, we will review for DLTs after completion of the 90 day DLT window and enroll 3 additional subjects at 75 Gy if DLT has been observed in 1 subject, or terminate the trial if $\geq 33\%$ DLT were observed among the first three subjects at 75 Gy. For the next group of three subjects at 75 Gy, we will review DLT/toxicity after all three subjects have completed the 90 days DLT window. We will additionally describe rates of complications and toxicity (i.e., acute and late overall, GU and GI) by grade and by dose once the 6 month follow-up period is complete for all subjects. Toxicities among those not receiving EBRT will not affect the MTD determination or the decision to enroll additional patients at the same dose or at a higher dose. The DMC will review data at least once annually.

If the DMC recommends termination of the study we will terminate the study. If in the first subject at any dose Grade 4-5 hematuria, proctitis or fistula occur, we will terminate the study. If $\geq 33\%$ of subjects experience DLT (i.e., Grade 3 hematuria, proctitis, urinary retention) within the first 90 days post EBRT, the trial will be closed.

The Clavien-dindo classification of surgical complications will be used to assess complications and the NCI-CTCAE v4.0 in addition to the RTOG acute and late morbidity scoring criteria will be used to grade adverse events and toxicity.

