- b. An investigator brochure, package insert, or device labeling is revised to indicate an increase or magnitude of a previously known risk, or describes a new risk.
- c. Withdrawal, restriction, or modification of a marketed approval of a drug, device, or biologic used in research protocol
- d. Protocol deviation or violation that harmed subjects or others or that indicated subjects or others might be at increased risk of harm.
- e. Complaint of subject that indicates subjects or others might be at increased risk of harm or at risk of a new harm
- f. Any breach in confidentiality that may involve risk to the subject or others.
- g. Any harm experienced by a subject or other individual that in the opinion of the investigator is unexpected and at least probably related to the research procedures.

- Routine Reporting

All other adverse events- such as those that are expected, or are unlikely or definitely not related to the study participation- are to be reported annually as part of regular data submission.

- Stopping Rules

If the DMC recommends termination of the study we will terminate the study. If in the first subject at any dose Grade 4-5 hematuria, proctitis or fistula occur, we will terminate the study. If $\geq 33\%$ of subjects experience DLT at any dose level (i.e., Grade 3 hematuria, proctitis, urinary retention) within the first 90 days post EBRT, the trial will be closed.

- In accordance with local IRB requirements, the following information will be reported within five (5) business days.
 - Non-compliance with federal regulations governing human research or with the requirements or determinations of the IRB, or an allegation of such non-compliance
 - Failure to follow the protocol due to the action or inaction of the investigator or research staff.

[Type here]

Protocol Title:	A Phase I Single-Arm Open Label Dose-Escalation Study of CivaSheet with Radical Prostatectomy with or without Adjuvant External Beam Radiation Therapy in Patients with High Risk Prostate Cancer
Principal Investigator Name/Contact Info:	[name]/ [contact]/ [contact]
Primary Contact Name/Contact Info	[contact] [name]
Date Revised:	7/22/2022
Study Number:	GCO#1: 16-1314

- Breach of confidentiality
- Premature suspension or termination of the research by the sponsor or investigator.

g) Withdrawal of Subjects:

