While all genitourinary and gastrointestinal toxicities according to the NCI-CTCAE will be documented and evaluated every time a subject is seen Grade 3-5 hematuria, urinary retention and rectal bleeding/radiation proctitis are the specific toxicities used for dose escalation procedures. This study defines DLT as the development of NCI-CTCAE Grade >3 urinary retention, Grade 3 hematuria or Grade 3 rectal bleeding/radiation proctitis within 90 days post EBRT which is given 6 weeks after RP + Civasheet implant for 5 weeks. Grade 3 hematuria according to the NCI-CTCAE is defined as gross hematuria with indications including transfusion, IV medications, hospitalization, elective endoscopic, radiologic or operative intervention and limiting self-care activities for daily living. Grade 3 urinary retention is defined as an incomplete ability to empty the bladder with indications including elective operation or radiologic intervention, substantial loss of affected kidney function or development of mass. Grade 3 rectal bleeding/proctitis is defined as severe symptoms; fecal urgency or stool incontinence and limiting self-care activities for daily living. If > 33% of subjects experience these DLT at any dose, the dose level below that level will be considered the MTD. If  $\geq 33\%$  subjects experience a DLT at 60 Gy, the trial will be closed and no additional subjects will be enrolled. Also, if the first subject enrolled at 60 Gy experiences NCI-CTCAE Grade 4 or higher hematuria, fistula formation or proctitis, no additional subjects will be enrolled and the trial will be closed. If the first subject enrolled at 75 Gy experiences Grade 4 or higher hematuria, fistula formation or proctitis, no additional subjects will be enrolled at 75 Gy and 60 Gy will be considered the MTD. Grade 4 hematuria is defined as hematuria with life-threatening consequences and urgent radiologic or operative intervention indicated. Grade 4 or higher fistula (anal or urinary) formation is defined as a fistula with life-threatening consequences with urgent radiologic or operative intervention indicated. Grade 4 or higher proctitis is defined as proctitis with life-threatening consequences and urgent intervention indicated. The time frame for DLT evaluation is the first 90 days after EBRT. EBRT is given 6 weeks after RP+ Civasheet implant at 45 Gy in 25 fractions (Monday-Friday for 5 weeks). If > 33 % of subjects experience DLT at any dose level, the dose level below that level will be

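### A Grade 4+ fistula or treatment-related death in subjects 2 to 6 at a dose does not count as a DLT, although it stops the dose or the trial in subject 1

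*SAP*

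**What the plan says.** **What counts as a DLT.** The SAP (Primary Outcome) defines DLT as Grade 3 or worse urinary retention, hematuria or rectal bleeding/proctitis within 90 days after EBRT, and says "Grade 3-5 hematuria, urinary retention and rectal bleeding/radiation proctitis are the specific toxicities used for dose escalation procedures". The protocol's Stopping Rules name the same three: "at any dose level (i.e., Grade 3 hematuria, proctitis, urinary retention". Its safety-monitoring text, ahead of the Adverse Events section, does likewise. None of these lists includes fistula or death.

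**First-subject rules.** Protocol section 3(c), Number of Subjects, says "If in the first subject, Grade 4-5 hematuria, fistula formation, proctitis or death occurs in the DLT window, the trial will be terminated". For the first subject at 75 Gy the consequence is "fistula formation, proctitis or death occurs in the DLT window, 60 Gy will be considered the MTD". The safety-monitoring text and the Stopping Rules have a version without death: "If in the first subject at any dose Grade 4-5 hematuria, proctitis or fistula occur, we will terminate the study". The SAP's first-subject rules also name fistula and omit death.

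**Later subjects.** From the second subject on, section 3(c) counts DLTs only. A dose fails at 33% or more. At the top dose the rule is "< 33% of subjects experience DLT at 75 Gy, 75 Gy will be considered the MTD".

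**Replacement.** Section 3(c) adds that if a subject is withdrawn "prior to completing the entire DLT window without experiencing a DLT prior to withdrawal, an additional subject may be added to that dose level".

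**Monitoring.** Fistula is already on the list of surgical adverse events to be followed: "bowel perforation, erosion into surrounding structures, bleeding, fistula, worse rates of continence and erectile function".

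**The concern.** The plan treats a Grade 4+ fistula as grave enough to stop on one case, and the SAP describes it as life-threatening. From the second subject on, that event scores zero while a Grade 3 urinary retention scores one. The same holds for a treatment-related death that is not graded under a listed toxicity.

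The MTD is the primary outcome, and the SAP describes it as the highest dose without unacceptable toxicity. If the count omits events that the plan itself calls unacceptable, a dose can be declared tolerable on a count that does not describe what happened. Replacement makes this worse: a subject withdrawn after a Grade 4 fistula has had no DLT on paper, and the text does not say whether he stays in the denominator.

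**Working it through.** **Counting by the written rule** (section 3(c): six subjects per dose, the dose passes below 33%, so at most 1/6):

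| Events in subjects 2 to 6 | Score as written | Result | Score if counted | Result |
|---|---|---|---|---|
| Two Grade 4 fistulas, no listed toxicity | 0/6 | passes | 2/6 = 33.3% | fails |
| One Grade 4 fistula and one listed DLT, different subjects | 1/6 = 16.7% | passes | 2/6 = 33.3% | fails |
| One Grade 4 fistula with Grade 3 proctitis, same subject | 1/6 | passes | 1/6 | passes |

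At 2/6 a dose fails both the protocol's cutoff (33% or more) and the SAP's (above 33%).

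**The plan's own figures.** Section 3(c) prints escalation probabilities of 0.96, 0.87, 0.69, 0.50 and 0.31 at true risks of 0.1 to 0.5. They reproduce within 2 points if a dose escalates on 0/3, or on 1/3 followed by at most 1/3:

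(1−p)³ + 3p(1−p)²·[(1−p)³ + 3p(1−p)²] = 0.965, 0.856, 0.689, 0.496, 0.313.

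That allows 2/6. The written rule (at most 1/6) gives (1−p)⁶ + 6p(1−p)⁵ = 0.886, 0.655, 0.420, 0.233, 0.109. The mismatch is a separate matter. The written rule is used below.

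**Inputs for the size**
- p = 0.10, risk of a listed DLT: the low end of the protocol's 10–50% range, taken as Grade 3, so it does not trigger the first-subject stop.
- q = risk per subject of a Grade 4+ fistula or treatment-related death. The documents give no rate; 1%, 2%, 5% and 10% are assumptions.
- The first-subject stop applies in both versions.

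**Formulas, with no overlap between the two kinds of event (upper bound on the gap)**
- As written: p(1−p)⁵ + (1−p−q)[(1−p)⁵ + 5p(1−p)⁴]
- Counted, with t = p + q: p(1−t)⁵ + (1−t)[(1−t)⁵ + 5t(1−t)⁴]

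For q = 0.02:
- As written: 0.1×0.5905 + 0.88×(0.5905 + 0.3281) = 0.0590 + 0.8083 = 0.867
- Counted (t = 0.12): 0.1×0.5277 + 0.88×(0.5277 + 0.3598) = 0.0528 + 0.7810 = 0.834

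| q | As written | Counted | Gap (points) | Passes with two or more uncounted events |
|---|---|---|---|---|
| 1% | 0.877 | 0.860 | 1.7 | 0.1% |
| 2% | 0.867 | 0.834 | 3.4 | 0.4% |
| 5% | 0.840 | 0.754 | 8.6 | 2.0% |
| 10% | 0.794 | 0.623 | 17.1 | 6.9% |

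The last column comes from enumerating all 3⁶ outcome sequences. The rest of the gap (3.0, 6.5 and 10.2 points at 2%, 5% and 10%) is one uncounted event plus one listed DLT.

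**Sensitivity, p = 0.10** (as written/counted, or gap in points)

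| Variation | q = 2% | q = 5% | q = 10% |
|---|---|---|---|
| Events independent of listed DLTs | 0.868/0.838 | 0.841/0.765 | 0.797/0.645 |
| Half of the events come with a listed DLT | 1.6 | 4.0 | 7.8 |
| All events come with a listed DLT | 0 | 0 | 0 |

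With p = 0.20 and no overlap, the pairs are 0.641/0.601, 0.618/0.522 and 0.582/0.403.

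**The case against.** Five points can be made for the plan.

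1. **A stricter rule for the first subject is legitimate sentinel design.** This stands, and the fix keeps it. It does not explain why the event should score zero rather than one afterwards.
2. **Other safeguards exist.** The monitoring committee can stop the trial and its recommendations are binding; unexpected harm that is at least probably related goes to the IRB within five business days. A trial stopped that way would not escalate. But these routes are discretionary and leave the DLT fraction unchanged.
3. **The size rests on assumed rates and on a choice of overlap and rule.** This stands. Rare events or frequent overlap with proctitis or bleeding make the effect small. The safety-monitoring text would move from 60 to 75 Gy after 0/3; on that route the no-overlap gap at 2% is 2.6 points. Under the 2/6 allowance behind the printed table it is about 1 point at 2% and 3 points at 5%, but that allowance contradicts the written cutoff.
4. **Choosing DLT components is a clinical decision.** The protocol also monitors perforation and erosion, and a Grade 3 fistula would still score zero after the fix. That is so. The argument covers only events that the plan itself makes stopping events.
5. **A subject who dies or is withdrawn might be replaced rather than scored zero.** Possible, since the text is silent. Either way, the event does not enter the DLT count.

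**Conclusion.** The concern holds. The gap is definitional and follows from the text alone: read literally, two life-threatening fistulas among subjects 2 to 6 pass a dose at 0/6.

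How much it matters depends on a rate that the documents do not give. With a 10% listed DLT risk, six subjects and the 1/6 limit, the chance of passing a dose is overstated by at most 1.7 points at an assumed 1% event risk and 17.1 points at 10%. It is less with overlap and nil if every such event comes with a listed DLT. This should be fixed because it sits in the primary endpoint of a safety trial, even though the numerical effect is small if these events are rare.

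**What to change.** Use one DLT definition in the SAP Primary Outcome, protocol section 3(c), the safety-monitoring text and the Stopping Rules. A DLT is any of these within the DLT window:

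- urinary retention, hematuria, or rectal bleeding/proctitis of CTCAE v4.0 Grade 3 or worse;
- fistula of Grade 4 or worse;
- death rated possibly, probably or definitely related to study treatment (categories the protocol already has).

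State that a death rated unrelated is not a DLT. In the replacement paragraph of section 3(c), say that a subject with any of these events is evaluable and is not replaced.

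Keep the first-subject stop as a deliberately stricter rule covering any death, as section 3(c) has it, and add death to it in the safety-monitoring text, the Stopping Rules and the SAP. While editing, correct two slips in the SAP: one sentence sets the retention threshold above Grade 3 instead of at Grade 3 or higher, and one first-subject rule names prostatitis where proctitis is meant.

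**Cost.** A protocol and SAP amendment to a component of the primary endpoint, IRB approval, and re-scoring of events already recorded in the DLT window. No new data are needed: fistula is monitored and deaths are serious adverse events. The chance of escalation falls slightly, from 0.867 to 0.834 at most at an assumed 2% event risk with p = 0.10.

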All screening procedures must be performed within 30 days prior to registration unless otherwise stated. The screening procedures include informed consent, obtaining complete medical, surgical and infection history, demographic data, review of subject eligibility criteria, review of previous and concomitant medications, physical exam including height, weight and vital signs (temperature, pulse, respirations, blood pressure), baseline adverse event

Type here]

Protocol Title:	A Phase I Single-Arm Open Label Dose-Escalation Study of CivaSheet with Radical Prostatectomy with or without Adjuvant External Beam Radiation Therapy in Patients with High Risk Prostate Cancer
Principal Investigator Name/Contact Info:	[name]/ [contact]/ [contact]
Primary Contact Name/Contact Info	[contact] [name]
Date Revised:	7/22/2022
Study Number:	GCO#1: 16-1314

identification, complete blood count test, serum chemistries via a comprehensive metabolic pattern (including albumin, creatinine, etc.), an MRI prior to surgery if not already obtained prior to surgery and completion of the international index of erectile function questionnaire.

Procedures During Treatment

Prior to Treatment

- Physical exam, vital signs
- Hematology
- Serum chemistries

Day 1

- Radical Prostatectomy + Civasheet implant
- X-Ray for baseline assessment of Civasheet stability

1 week after RP + Civasheet Implant

- Physical exam, vital signs
- Hematology
- Serum chemistries
- Pathology Review
- JP Drain and Catheter removal

1 Months After RP + Civasheet Implant

- CT Scan for assessment of Civasheet stability, assessment of cancer recurrence and also for EBRT planning among those with adverse pathologic features who will undergo EBRT

3 and 6 Months After RP + Civasheet Implant

- CT Scan for assessment of Civasheet stability and assessment of cancer recurrence among those with adverse pathologic features who will undergo EBRT.

6 weeks after RP+ Civasheet Implant

- EBRT given at 45 Gy in 25 fractions for 5 weeks (Monday- Friday) among those with adverse pathologic features at EBRT.

[Type here]

Protocol Title:	A Phase I Single-Arm Open Label Dose-Escalation Study of CivaSheet with Radical Prostatectomy with or without Adjuvant External Beam Radiation Therapy in Patients with High Risk Prostate Cancer
Principal Investigator Name/Contact Info:	[name]/ [contact]/ [contact]
Primary Contact Name/Contact Info	[contact] [name]
Date Revised:	7/22/2022
Study Number:	GCO#1: 16-1314

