A Phase I Single-Arm Open Label Dose-Escalation Study of CivaSheet With Radical Prostatectomy With or Without Adjuvant External Beam Radiation Therapy in Patients With High Risk Prostate Cancer

[name]

NCT03657108

Document Date: 10-18-2022

**Primary Outcome:** We will determine the MTD for Civasheet when administered with RP and adjuvant EBRT. MTD is defined as the highest dose of the Civasheet® not yielding unacceptable toxicity. Specifically if > 33 % of subjects experience DLT at any dose level, the dose level below that level will be considered the MTD. Or if the highest level (75 Gy) has been reached and < 33% of subjects have experienced DLT, 75 Gy will be considered the MTD.. The present study defines dose limiting toxicity as the development of Grade 3 or higher (According to the NCI'S CTCAE v 4.0) urinary retention, hematuria or rectal bleeding/radiation proctitis within 90 days post EBRT which is given 6 weeks after RP + Civasheet implant for 5 weeks. Toxicities experienced among those not receiving adjuvant EBRT will not be used in the determination of the MTD. Binary or categorical outcomes will be described with proportion and 95% confidence intervals and continuous measures will be summarized with mean (SD) or median (IQR), as appropriate.

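### The documents do not agree on when DLT counting starts, and their exclusion and replacement wording can leave DLT-type events out of the MTD decision

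*SAP*

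**What the plan says.** **Window.** The SAP (Primary Outcome) places DLTs within 90 days of EBRT and then adds: "The time frame for DLT evaluation is the first 90 days after EBRT". Protocol section 3(c) counts three months from completion of EBRT and makes further enrolment wait: "Once the entire DLT window (i.e., 90 days post EBRT) is complete for this first subject". The safety-monitoring text and the Stopping Rules use the same 90 days. One paragraph of section 3(c) instead gives 30 days after EBRT for the observation cycle.

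**Earlier DLTs.** Section 3(c) also says: "Subjects missing doses due to a DLT will not be replaced since these subjects will be considered to have experienced a dose limiting toxicity". It allows a subject who leaves before the end of therapy, or before the end of the window, to be replaced if no DLT came first. Under the heading for 90 days after EBRT, the protocol asks for the cumulative DLTs.

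**Timing.** Procedures During Treatment puts the implant on Day 1 and, six weeks later, "EBRT given at 45 Gy in 25 fractions for 5 weeks".

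**Exclusion.** Section 3(c) gives a pathology reason: "patients without these adverse pathologic features at RP will be replaced with additional patients at that dose level". It then closes: "The MTD will only be determined for patients undergoing RP + Civasheet implant + adjuvant EBRT". The safety-monitoring text says: "Toxicities among those not receiving EBRT will not affect the MTD determination or the decision to enroll additional patients at the same dose". The SAP says: "Toxicities experienced among those not receiving adjuvant EBRT will not be used in the determination of the MTD". These last three give no reason for the missing EBRT.

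**Unknown DLT status.** The Follow-Up provisions for patients seen outside the health system drop a subject who cannot come in when a visit is needed to judge DLTs. They replace a subject who does not respond to two contact attempts.

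**The concern.** The MTD is the primary outcome, and it rests on a count of at most six subjects per dose. If the documents disagree on whether an event before the end of EBRT can be a DLT, two people applying them in good faith can reach different counts from the same data. The exclusion and replacement wording points the same way. Leaving out a subject with an event lowers the observed DLT count, or leaves it unchanged if the replacement also has a DLT. It never raises it. Escalation to 75 Gy could then follow when full counting would have stopped the trial.

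The opposite error is also possible. Counting from the implant without an attribution rule could turn surgical complications into DLTs; the protocol lists bleeding and fistula among the surgical events it monitors.

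**Working it through.** **1. Timeline.** Six weeks to EBRT (42 days) plus five weeks of EBRT (35 days) gives day 77 after implant. Adding 90 days gives day 167. Read literally, the window runs from about day 77 to day 167.

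**2. The passages side by side.** Take a Grade 3 hematuria in week 8 that interrupts EBRT.
- Section 3(c), missed doses: a DLT, and the subject is not replaced. The implant is a single procedure, so the doses that can be missed are EBRT fractions, all scheduled before day 77.
- SAP time frame, and section 3(c) counting from EBRT completion: outside the window, so not a DLT.
- SAP, within 90 days of EBRT: either, depending on whether this is a start or only a cut-off.
- If a similar event came before EBRT and no EBRT were given, the literal exclusion would also remove the subject from the MTD count.

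**3. The plan's own escalation figures.** Let q be the chance that a subject is counted as a DLT.
- Text rule of section 3(c): stop at 2 of the first 3, otherwise treat 6, escalate at 1 of 6 or fewer. E = (1−q)^6 + 6q(1−q)^5. At q = 0.40: 0.047 + 0.187 = 0.233.
- Table-fitting rule: escalate at 0 of 3; at 1 of 3 add three and escalate if at most one of those has a DLT, so 2 of 6 passes. E = (1−q)^3 + 3q(1−q)^2 × [(1−q)^3 + 3q(1−q)^2]. At q = 0.40: 0.216 + 0.432 × 0.648 = 0.496.

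| True risk | 0.1 | 0.2 | 0.3 | 0.4 | 0.5 |
|---|---|---|---|---|---|
| Printed in section 3(c) | 0.96 | 0.87 | 0.69 | 0.50 | 0.31 |
| Table-fitting rule | 0.965 | 0.856 | 0.689 | 0.496 | 0.313 |
| Text rule | 0.886 | 0.655 | 0.420 | 0.233 | 0.109 |

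The printed table agrees within 2 points with a rule that lets 2 of 6 pass. It does not agree with the text, which stops at 2 of 6 (33.3%).

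**4. One omitted event, no assumed share.** Suppose two of six subjects at 60 Gy have DLT-type events and one is uncounted. Under the text rule:
- kept as a non-event: the count is 1 of 6 (17%), and the trial escalates with certainty;
- replaced by a fully counted subject: it escalates if the new subject has no DLT, probability 1 − p, which is 0.80 at p = 0.20 and 0.60 at p = 0.40.

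Under the table-fitting rule, one event in each group of three escalates whether or not one is omitted, so the decision need not reverse.

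**5. Illustration only.** Assume a share f of true DLTs is uncounted. If the subject is kept, q = p(1−f); if replaced, q = p(1−f)/(1−pf). Cells give the escalation probability, kept / replaced.

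| Rule, true risk p | f = 0 | f = 10% | f = 25% |
|---|---|---|---|
| Text, 0.20 | 0.655 | 0.704 / 0.695 | 0.776 / 0.758 |
| Text, 0.40 | 0.233 | 0.301 / 0.274 | 0.420 / 0.351 |
| Table-fitting, 0.40 | 0.496 | 0.574 / 0.545 | 0.689 / 0.626 |

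If the protocol's true risk means in-window events only, early events add to it. With in-window risk 0.20 and an assumed extra early risk of 0.05 or 0.10, the text rule escalates with probability 0.655 when early events are ignored, against 0.534 (q = 0.25) or 0.420 (q = 0.30) when they are counted.

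**The case against.** The strongest reply is that the 90 days is a cut-off, not a start. The SAP's opening definition can be read so, and the cumulative assessment and the missed-dose sentence fit that reading. This stands as far as it goes: the documents do not establish that counting starts only after EBRT. But the SAP's time-frame sentence and the protocol's count from EBRT completion do not fit it, so the conflict remains.

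On the exclusion, the protocol ties EBRT to pathology and Tables 1 and 2 show only two pathways, so subjects without EBRT may simply mean the pathology group. A subject who stops partway has received EBRT and is not caught. That also stands. A reader might infer that the plan discards subjects whose EBRT was withheld for toxicity, but no passage describes such a case. What is left is a wording gap that matters mainly for events before EBRT.

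On missing status, replacing subjects who cannot be evaluated is usual in a 3+3 design. Section 3(c) protects a DLT seen before withdrawal, reasons for removal are documented, follow-up continues unless consent is withdrawn, and an intent-to-treat analysis is planned. Serious events go to the principal investigator within 24 hours, and unexpected events go to the monitoring board. These are real safeguards, but none says how an unresolved subject enters the MTD count.

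**Conclusion.** The point holds as a contradiction about when DLT counting starts, with two related wording gaps, and it should be fixed. The same Grade 3 event during EBRT is a DLT under one sentence of section 3(c) and not under the SAP's time frame.

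The size is unknown. The documents give no rate of early events and no expected number of subjects with unresolved DLT status; if no event goes uncounted, nothing changes. The 10% and 25% shares are assumptions. The reversal from one omission needs no assumed share, but it depends on the text rule.

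Two stronger readings should be resisted. A reader might take 77 of 167 days (46%) as the share of toxicity missed. That is elapsed time, not risk, and Table 1 records toxicity from Day 1. A reader might also infer that one omission always reverses the decision. Under the rule that fits the printed table it need not.

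**What to change.** 1. Reconcile section 3(c) (including its 30-day sentence), the assessment at 90 days after EBRT, the safety-monitoring text, the Stopping Rules and the SAP to one stated start and end of DLT counting, with a stated rule for attributing surgical complications. Reconcile the first-subject rule too. Section 3(c) and the safety-monitoring decision text tie it to the window, while the stopping sentences and the SAP state no period; only section 3(c) lists death. Which clinical rule applies is for the investigators. Bring the escalation text and its printed table into agreement.
2. In section 3(c), the safety-monitoring text and the SAP, limit the exclusion and replacement to subjects who omit EBRT for lack of adverse pathologic features. Apply the no-replacement sentence consistently with the period settled in item 1.
3. For subjects dropped, withdrawn or lost before DLT status is known, for a possibly toxicity-related reason, run a sensitivity count that treats them as DLTs before each escalation or MTD decision. Give it to the DSMC with the main count, and state in advance how a disagreement is handled.

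The cost is wording in both documents and one small analysis. Toxicity is already collected from Day 1 and reasons for non-compliance are already documented, so no visits are added. The downside is that the observed DLT rate and the chance of stopping may rise, some surgical events will need attribution, and with six subjects one person can change the sensitivity result.
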